3.2 Treatment with Additional Cycles Beyond 24 Weeks

All subjects will be treated for 24 weeks (up to 3 cycles) of monotherapy (Parts A or C) or combination therapy (Parts B or D) unless criteria for study drug discontinuation are met earlier ([Section 3.11](#)). All subjects completing approximately 24 weeks of treatment with ongoing disease

control (CR, PR or SD) or unconfirmed PD, may be eligible for an additional 3 cycles of study therapy in both monotherapy (Parts A and C) and combination therapy (Parts B D and E) beyond the initial 24 weeks, on a case-by-case basis, after careful evaluation and discussion with the BMS Medical Monitor to determine whether the risk/benefit ratio supports administration of further study therapy. All subjects completing approximately 48 weeks of treatment with ongoing disease control (CR, PR or SD) or unconfirmed PD, may be eligible for an additional 7 cycles of study therapy in combination therapy (Parts D and E) beyond the initial 48 weeks, on a case-by-case basis, after careful evaluation and discussion with the BMS Medical Monitor to determine whether the risk/benefit ratio supports administration of further study therapy. For patients who present with PD for the first time at the end of cycle 6, please contact the Medical Monitor for discussion. Upon completion of 3 cycles of study therapy (or up to a maximum of 13 cycles if applicable), all subjects will enter safety follow-up period.

3.3 Follow-up

3.3.1 Safety Follow-up

Upon completion of 3 cycles of study therapy (or up to a maximum of 6 cycles if applicable), all subjects will enter safety follow-up period once the decision is made to discontinue the subject from treatment (e.g., at end of treatment [EOT]).

[figure not shown]
For subjects that complete all scheduled cycles of therapy, EOT visit will be the same as the last scheduled and completed on-treatment visit, and the start of week 1 safety follow up visit. For subjects that do not complete all scheduled cycles of therapy, EOT visit will be the most recent on-treatment visit (with all available safety and response data) and does not need to be repeated, and will be considered the start of week 1 safety follow up visit.

After the EOT visit, all subjects will be evaluated for any new AEs for at least 100 days after the last dose of therapy. Follow-up visits should occur at Days 30, 60 and 100 (± 7 days) after the last dose or coinciding with the date of discontinuation (± 7 days) if date of discontinuation is greater than 30 days after the last dose to monitor for AEs. All subjects will be required to complete the 3 clinical safety follow up visits regardless of whether they start new anti-cancer therapy, except those subjects who withdraw consent for study participation.

The study design schematic is presented in [Figure 3.3.1-1](#).

Figure 3.3.1-1: Study Schematic

FIH Overall Schematic (mono/combo)

CR = complete response; PR = partial response; SD = stable disease; PD = progressive disease

Physical examinations, vital sign measurements, 12-lead ECG, and clinical laboratory evaluations will be performed at selected times throughout the dosing interval. Subjects will be closely monitored for AEs throughout the study. Blood will be collected for up to 29 days at specified times (Section 5.5) after study drug administration for PK analysis.

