In Part B, combination therapy dose escalation, the planned dose levels for BMS-986156 are 10, 30, 100, 240, and 800 mg Q2W in combination with nivolumab, which will be administered at a dose of 240 mg Q2W, in 8-week cycles, for up to 3 cycles of study therapy. The Sponsor chose 30 mg BMS-986156 in combination with 240 mg nivolumab as the starting dose in Part B, based on the safety profile of Part A (monotherapy dose escalation). No DLT nor any AE (greater than Grade 1), for which no other cause than the investigational drug could be identified, had occurred.

Starting dose level of BMS-986156 was determined based on safety, pharmacokinetics (PK), [REDACTED] and is one dose level lower than the dose already tolerated Part A (ongoing monotherapy dose escalation).

In Part C, a monotherapy tumor-specific cohort expansion will be carried out at the BMS-986156 monotherapy dose selected from Part A (monotherapy dose escalation), which may represent the maximum tolerated dose (MTD), maximum administered dose (MAD), or an alternate dose(s). Study therapy will be administered Q2W, in 8-week cycles, for up to 3 cycles.

In Part D, a combination therapy cohort expansion will be carried out using the combination dose of BMS-986156 selected from Part B, 240 mg BMS 986156 in combination with 240 mg nivolumab, Q2W dosing, and may represent the MTD, MAD, or an alternate dose(s) for the combination. Study therapy will be administered Q2W, in 8-week cycles, for up to 3 cycles.

In Part E, a combination therapy cohort expansion, exploring Q4W dosing, will be carried out using the combination dose of 480 mg BMS 986156 with 480 mg nivolumab, in cervical cancer (cohort 9) and other tumor types (Cohort 10). Each cohort in Part E will consist of approximately 40 subjects each. Study therapy will be administered Q4W, in 8-week cycles, for up to 3 cycles.

Study Phase: Phase 1/2a

Research Hypothesis: It is anticipated that anti-GITR antibody (BMS-986156), administered as a single agent or in combination with nivolumab, will demonstrate adequate safety and tolerability, as well as a favorable risk/benefit profile, to support further clinical testing. No prospective hypotheses are being formally evaluated.

Objectives:

Primary Objective:

The primary objective is to determine the safety, tolerability, dose-limiting toxicities (DLTs), and MTD/MAD/alternate dose(s) of BMS-986156 administered alone and in combination with nivolumab in subjects with advanced solid tumors.

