The treatment phase consists of up to three 8-week treatment cycles. In Parts A and C, each treatment cycle comprises 4 doses of BMS-986156 administered every 2 weeks on Days 1, 15, 29, and 43 of the treatment cycle. In Parts B and D, each treatment cycle comprises 4 doses of BMS-986156 (administered on Days 1, 15, 29 and 43) in combination with 4 doses of nivolumab administered on Days 1, 15, 29, and 43 of the treatment cycle. In Parts B and D and E when both study drugs are given, nivolumab will be given first followed by BMS-986156 at least 30 minutes after completion of the infusion of nivolumab. In Part E, the cohort of 480 mg/480 mg each treatment cycle comprises 2 doses of BMS-986156 (administered on Days 1 and 29) in combination with 2 doses of nivolumab administered on Days 1 and 29 of the treatment cycle.

Following each treatment cycle, the decision to treat a subject with additional cycles of study therapy, up to a maximum of 13 treatment cycles, will be based on tumor assessment (evaluation performed between Days 49 and 56 of each cycle and completed before the first dose in the next cycle). Tumor progression or response endpoints will be assessed using Response Evaluation Criteria in Solid Tumor (RECIST) v1.1 criteria for solid tumors ([Appendix 3](#)).

Treatment beyond progression may be allowed in select subjects with initial RECIST v1.1-defined progressive disease (PD) after discussion and agreement with the BMS Medical Monitor that the benefit/risk assessment favors continued administration of study therapy (e.g., subjects are continuing to experience clinical benefit as assessed by the Investigator, tolerating treatment, and meeting other criteria specified in [Section 3.11.1.1](#)).

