Subjects with a response of unconfirmed PD, SD, partial response (PR), or complete response (CR) at the end of a given cycle will continue to the next treatment cycle. Subjects will generally be allowed to continue study therapy until the first occurrence of either: 1) completion of the maximum number of cycles, 2) confirmed PD, 3) clinical deterioration suggesting that no further benefit from treatment is likely, 4) intolerability to therapy; or 5) the subject meets criteria for discontinuation of study therapy as outlined in protocol [Section 3.11](#). Individual subjects with confirmed CR will be given the option to discontinue study therapy on a case by case basis after specific consultation and agreement between the Investigator and BMS Medical Monitor in settings where benefit/risk justify discontinuation of study therapy.

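### Section 3.3.1 caps treatment at 6 cycles for every subject while Section 3.2 allows 13 in Parts D and E, and Section 3.1 gives 13 without limiting it to those Parts

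*Combined protocol and SAP*

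**What the plan says.** **Cycle maximum.** Section 3.3.1 (Safety Follow-up) sets the limit for entry to follow-up as "or up to a maximum of 6 cycles if applicable), all subjects will enter safety follow-up period once the decision is made to discontinue". Section 3.2 (Treatment with Additional Cycles Beyond 24 Weeks) ends with the parallel sentence: "or up to a maximum of 13 cycles if applicable), all subjects will enter safety follow-up period". Section 3.1 (Treatment Phase) allows "up to a maximum of 13 treatment cycles" and names no Part. The columns of Table 5.1-2 cover cycles 1 to 13.

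**How 13 is built.** Section 3.2 gives 24 weeks (3 cycles) at first, then up to 3 further cycles for Parts A, B, C, D and E, then an "additional 7 cycles of study therapy in combination therapy (Parts D and E) beyond the initial 48 weeks". Only Parts D and E have the last step. Both extensions are decided subject by subject with the Medical Monitor.

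**Why the maximum matters.** Section 3.1 lists, among the events that end study therapy, "1) completion of the maximum number of cycles, 2) confirmed PD".

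**Part E.** The synopsis says of Part E: "Study therapy will be administered Q4W, in 8-week cycles, for up to 3 cycles". Its sentence on weeks 24 to 48 names Parts A, C, B and D but not E, yet its next sentence offers cycles after week 48 to Parts D and E. In Section 3.2 the opening sentence on the initial 24 weeks refers to monotherapy (Parts A or C) or "combination therapy (Parts B or D) unless criteria for study drug discontinuation are met earlier", again without Part E.

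**Duration.** The synopsis expects about 3.1 years for any subject, monotherapy or combination. The current text has three periods: screening (up to 28 days), treatment, and a safety follow-up of 100 days.

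**The concern.** The maximum number of cycles is a stopping rule, so it should have one value for each Part. It does not. A site reading 3.3.1 for a Part D or E subject with disease control at week 48 would conclude that treatment is complete. The same site reading 3.2 would conclude that up to 7 more cycles can be requested. The reverse problem arises in Parts A to C: 3.1 appears to allow 13 cycles, while 3.2 provides no step beyond cycle 6.

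At stake is how long a subject is dosed and when the 100-day follow-up starts. The Part E omissions and the 3.1-year figure are lesser defects of the same kind, because they describe treatment length in ways that do not match the rule in 3.2.

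**Working it through.** **Inputs.** Cycle length 8 weeks = 56 days (3.1). Screening up to 28 days (3.1). Follow-up 100 days (synopsis; 3.3.1). Extension steps +3 and +7 cycles (3.2). Dosing days per cycle: 4 in Part D (Days 1, 15, 29, 43). In Part E, "each treatment cycle comprises 2 doses of BMS-986156 (administered on Days 1 and 29", that is, 2.

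**Step 1. Maximum by Part under 3.2.**
- Parts A, B, C: 3 + 3 = 6 cycles = 48 weeks.
- Parts D, E: 3 + 3 + 7 = 13 cycles = 104 weeks.

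**Step 2. Compare with the other sections.**

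| Source | Stated maximum | Parts A–C (3.2 gives 6) | Parts D–E (3.2 gives 13) |
|---|---|---|---|
| Section 3.3.1 | 6, all subjects | agrees | conflicts |
| Section 3.1 | 13, no Part named | conflicts | agrees |
| Table 5.1-2 | cycles 1 to 13 | one table for all Parts | agrees |

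**Step 3. Size of the conflict in Parts D and E.** 13 − 6 = 7 cycles; 7 × 8 = 56 weeks. Dosing days: 7 × 4 = 28 in Part D and 7 × 2 = 14 in Part E. These are maxima for a subject approved for every cycle. The documents do not say how many subjects that would be.

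**Step 4. Try to reproduce 3.1 years.** 3.1 × 365.25 = 1,132 days. Planned duration = 28 + 56 × cycles + 100.

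| Cycles | Days | Years | Short of 1,132 days by |
|---|---|---|---|
| 3 | 28 + 168 + 100 = 296 | 0.81 | 836 |
| 6 | 28 + 336 + 100 = 464 | 1.27 | 668 |
| 13 | 28 + 728 + 100 = 856 | 2.34 | 276 |

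To reach 3.1 years, (1,132 − 128) / 56 ≈ 18 cycles would be needed.

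**Step 5. Sensitivity at 13 cycles.**
- Follow-up visit at the end of its +7-day window: 863 days, 2.36 years.
- Follow-up counted from the last dose, Part D (Cycle 13 Day 43): 28 + 12 × 56 + 42 + 100 = 842 days, 2.31 years.
- The same for Part E (Cycle 13 Day 29): 28 + 12 × 56 + 28 + 100 = 828 days, 2.27 years.
- One 6-week dose delay: 856 + 42 = 898 days, 2.46 years.

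At 6 cycles, counting from the last dose gives 28 + 5 × 56 + 42 + 100 = 450 days, 1.23 years. None of these variants reaches 3.1 years.

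**Step 6. Part E.** Read literally, the synopsis gives Part E weeks 0 to 24 and the option after week 48, but nothing between. Section 3.2 names Part E for weeks 24 to 48, and the synopsis and 3.1 both give it its initial cycles. The intended path is therefore clear from the rest of the text.

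**The case against.** **The sentence in 3.3.1 is qualified, and it sits in the follow-up section.** It applies where applicable and once a decision to discontinue has been made. Section 3.2 is the section on treatment length, and 3.1 and Table 5.1-2 support its 13. Six is also the right number for Parts A to C. This lowers the risk of misreading but does not reconcile the limits: a stated maximum of 6 for all subjects excludes 13.

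**The Medical Monitor controls every extension.** This stands, and it is why the practical impact is modest. A reader might infer that Part D and E subjects have been, or will be, stopped at week 48. The documents do not support that, because the sponsor takes part in each decision and would apply 3.2. The schematic in 3.3.1 is not visible in the text reviewed and may show the right number.

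**The month-12 progression-free rate.** A reader might infer that a 6-cycle stop would leave the Section 8.4.3 estimate for the combination without scans. That goes too far. Table 5.1-3 places a tumor assessment at the 100-day follow-up visit. After a last dose on Cycle 6 Day 43, that visit falls 5 × 56 + 42 + 100 = 422 days after the first dose, which is past month 12.

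**Part E.** A reader might infer that Part E is barred from weeks 24 to 48. Section 3.2 says otherwise, so the omissions are editorial.

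**The 3.1 years is only an approximate expectation.** No analysis uses it. Dose delays can be extended with no stated cap (4.3.6), related adverse events are followed until they recover or are judged irreversible (5.3), and subjects enrolled earlier may have spent time in follow-up phases since removed. An individual's stay can therefore exceed 2.3 years. But none of this is planned time, and one figure cannot serve both arms when their maxima differ by 856 − 464 = 392 days. That the figure was carried over from the removed phases is plausible, but the documents do not show how it was derived.

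**Conclusion.** The inconsistency is real and lies in the current operative text. Section 3.3.1 is wrong for Parts D and E (6 instead of 13 cycles; 48 instead of 104 weeks). Section 3.1 is wrong for Parts A to C if its unrestricted 13 is taken at face value. This rests on treating the stepwise rule in 3.2 as the intended one, which is reasonable because it is the only place that builds the maximum Part by Part.

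It should be corrected because the maximum is a stopping rule, but a wrong stop is unlikely and no number of affected subjects can be given. The Part E omissions and the 3.1-year duration are minor. The planned maximum is about 2.3 years for Parts D and E and about 1.3 years for Parts A to C, counting full cycles and before dose delays or prolonged adverse-event follow-up. No sample size, confidence interval, endpoint or analysis is affected.

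**What to change.** **Main change.** In both 3.3.1 and 3.1, replace the single number with: *a maximum of 6 cycles for Parts A, B and C and 13 cycles for Parts D and E, per Section 3.2*. Correcting 3.3.1 alone would leave 3.1 in conflict with 3.2 for Parts A to C.

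**Accompanying corrections.**
- Add Part E to the synopsis sentence on the week 24 to 48 extension.
- Add Part E to the opening sentence of 3.2.
- Restate the synopsis duration per subject as up to about 2.3 years for Parts D and E and about 1.3 years for Parts A to C, before dose delays or extended adverse-event follow-up.

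**Cost.** Wording in five places, which can go into the next amendment or an administrative letter. Visits, sample size, endpoints and analyses stay as they are.

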3.4 Dose Escalation

3.4.1 Parts A and B

The dose-escalation phase of the study will evaluate the MTD/MAD/alternate dose(s) of BMS-986156 alone or in combination with nivolumab based on DLTs using a BLRM-Copula model, where the BLRM is designed to guide BMS-986156 monotherapy dose escalation and BLRM-Copula is for the dose escalation of BMS-986156 in combination with nivolumab. The Bayesian model will be used for recommendation of next dose level to be investigated. BLRM (-Copula) with overdose control (EWOC) principle¹⁴⁴ will be employed to ensure that safety is not compromised during dose escalation.

The initial dose level of BMS-986156 in Part A will be a flat dose of 10 mg as an IV infusion over 60 minutes every 2 weeks. Expected dose levels for dose escalation (determined by half log increments from starting dose)¹⁴⁷ are provided in [Table 3.4.1-1](#).

Starting dose selection of BMS-986156 for Part B will be determined using data available from all doses evaluated in Part A, including clinical and safety laboratory, PK, [REDACTED] and modeling recommendations within Bayesian hierarchical modeling framework by incorporating single agent toxicity profiles of both BMS-986156 (Part A) and nivolumab (CA209003, a Phase 1 nivolumab monotherapy data in advanced solid tumors); starting dose will be one dose level lower than a dose already tested and shown to be tolerated in ongoing monotherapy dose escalation in Part A [REDACTED]. A dose -1 cohort of 3 mg has been included and will only be explored in the event 10 mg dose of BMS-986156 is determined to exceed the MTD in monotherapy or in combination with nivolumab (Table 3.4.1-1).

Dose levels to be considered for the next cohort will be based on evaluating three potential recommendations by BLRM (-Copula): escalate, de-escalate, or stay at same dose level. Final dose selection for next cohort/dose level will be made in conjunction with the data available on all dosed subjects, including clinical and laboratory safety assessments, PK, [REDACTED] data, will not allow escalation by more than one dose level and will be made after discussion and agreement between Investigators and Medical Monitor. Accordingly, intermediate or lower doses, or less frequent dosing of BMS-986156 may be tested if none of the planned doses/schedules is found to be tolerated as monotherapy or in combination with nivolumab. Up to an additional 9 subjects may be enrolled in an already DLT cleared cohort to collect additional PK, [REDACTED] and safety data to better understand any dose response relationship.

Approximately 30 subjects each will be treated in each dose escalation phases in monotherapy (Part A) and combination therapy (Part B).

During dose escalation phase, once a dose level has been decided, a set of approximately 3 subjects will be treated at that specified dose level. Cohort tolerability assessment and subsequent dose recommendation will occur according to BLRM (-Copula) recommendation and after at least 2 subjects complete the 4 week DLT observation period. If the potential DLT occurring in the 3rd evaluable subject regarding the specific dose level does not influence the dose recommendation by BLRM (-Copula), the BLRM (-Copula) recommended next dose level may proceed without waiting for the 3rd subject to complete the corresponding DLT observation period, after discussion and agreement between Sponsor and Investigators.

Subjects must be observed for a total of 28 days following the first therapy dose to be considered evaluable for DLT. Subjects discontinued during DLT observation period due to DLT are also considered as evaluable for DLT. Continuous re-assessment of dose recommendation by BLRM (-Copula) will also be carried out at each dose levels.

The MTD/MAD/alternate dose(s) of BMS-986156 selected for cohort expansion in Parts C and D will be based on evaluating the recommendation from BLRM and a synthesis of all available data, including clinical and laboratory safety assessments, PK, [REDACTED] and efficacy data, from all treated patients at each dose level up to the MTD/MAD.

No intra-subject dose escalation or reduction is allowed.

Sentinel Subject (Parts A and B only): During dose escalation, a staggered dosing (sentinel subject) approach will be used for the first subject in the first dose level of both monotherapy and combination cohorts. Only applicable to the lowest dose level: The first subjects at the lowest dose levels in both Part A and Part B will receive Cycle 1 Day 1 dose (e.g., the first dose of study drugs) and be observed for 5 days before additional subjects in the cohort receive study drug (e.g., subject two onward are dosed). The first subjects to be dosed in subsequent cohorts will not be required to observe the 5-day interval between treatment start dates.

Table 3.4.1-1: Dose Escalation Schedule for Parts A and B^{a,b,c}

Dose Level	BMS-986156 Part A and Part B	Nivolumab Only Part B
-1	3 mg	240 mg IV Q2W
1	10 mg	240 mg IV Q2W
2	30 mg	240 mg IV Q2W
3	100 mg	240 mg IV Q2W
4	240 mg	240 mg IV Q2W
5	800 mg	240 mg IV Q2W

Abbreviations: IV, intravenous; MAD, maximum administered dose; MTD, maximum tolerated dose; PK, pharmacokinetics; Q2W, every 2 weeks.

^a Additional subjects may be added for a total of up to 12 subjects per selected dose levels to provide additional safety, tolerability and PK data. This information will be incorporated into final recommendation for MAD/MTD/alternate dose(s) of BMS-986156

^b Dose -1 (3 mg) will be evaluated if 10 mg (dose level 1) exceeds MTD

^c Starting dose for Part B will be one dose level lower than a dose already tested and shown to be tolerated in ongoing monotherapy dose escalation in Part A [REDACTED]

3.5 Cohort Expansion (Parts C, D, and E)

The purpose of cohort expansion is to gather additional safety, tolerability, preliminary efficacy, PK, [REDACTED] information regarding BMS-986156 as monotherapy or in combination with nivolumab.

Part C consists of cohort expansions with BMS-986156 monotherapy in 2 disease-restricted populations: (i) NSCLC subjects with progressive or recurrent disease (per RECIST v1.1) during or after anti-PD-1 or anti-PD-L1 therapy following prior platinum doublet-based chemotherapy and (ii) persistent, recurrent or metastatic cervical cancer.

Part D consists of cohort expansion with BMS-986156 administered in combination with nivolumab in disease-restricted populations: (i) NSCLC, (ii) cervical, (iii) bladder cancer, (iv) squamous cell carcinoma head and neck, (v) ovarian cancer, and (vi) HCC.

No more than 5 subjects previously found to be “rapid progressors” on anti-PD-1 or anti-PD-L1 therapy will be enrolled per cohort (see definition of “rapid progressors” in [Section 3.1](#)).

Each of the cohort in cohort expansion phase will contain approximately 40 subjects. (Please refer to more details in [Section 8.1.2](#)).

Parts E includes two cohorts with one as cervical and another for other solid tumors for signal seeking and exploration of Q4W dosing respectively. Due to the purpose of signal confirming in cervical cancer and heterogeneity of response rates of the other solid tumors cohort (I-O experienced NSCLC, ovarian cancer, bladder cancer, SCCHN, and HCC), approximately 40 subjects are planned for each cohort in part E. For initial safety evaluation of 480 mg BMS-986156/480 mg nivolumab Q4W 6 subjects for a safety lead-in will be enrolled and followed for a minimum of two weeks (refer to [Section 3.6](#) for the rationale for two week period) prior to opening full enrollment of Part E.

Table 3.5-1: Expansion Cohorts

Cohorts	Total Subjects (Approximate Number)
Part C: BMS-986156	
1	NSCLC
2	Cervical Cancer
Part D: BMS-986156 + Nivolumab	
3	NSCLC
4	Cervical cancer
5	Bladder
6	Squamous cell carcinoma head and neck
7	Ovarian Cancer
8	Hepatocellular
Part E: BMS-986156 + Nivolumab	
9	Cervical
10	Multiple solid tumor types

Abbreviation: NSCLC, non-small cell lung cancer.

Continuous evaluation of toxicity events in the cohort expansions will be performed throughout enrollment in the expansion cohorts. If at any time, the aggregate rate of treatment-related toxicities meeting DLT criteria exceeds 33% across all subjects treated across all cohorts treated within monotherapy and combination therapy phases at the same dose, the findings will be discussed and further enrollment may be interrupted. Depending on the nature and grade of the toxicity and after

assessing the risk/benefit ratio, a new dose(s) for all cohorts may be initiated at a previously tested lower dose level or at a dose level intermediate to previously tested lower dose levels.

